through the day of the last intervention session date (6 weeks later) and from intervention end date to 7 months later (8.5-month follow-up period in total). The interview window for postintervention assessment was 1 to 14 days after the intervention end, and for the follow-up assessment, the window was 7–9 months after the intervention end, and this variability was dependent on participant availability. This allowed for the quantification of daily substance use from study intervention start date to study end point. TLFB data allowed us to operationalize three substance use outcomes for any drug use and alcohol to intoxication as well as methamphetamine and cannabis/marijuana, including the following: time to first use, quantified as days until first any drug use or alcohol intoxication; days of use, quantified as the total number of days in which any drugs were used or alcohol intoxication occurred, and relapse status, quantified according to a) abstinent, did not use during the period after the study intervention; b) lapse, used after study intervention but did not revert to regular use on one-third or less of days after first use; and c) relapse, used substance after the study intervention and continued to use regularly on more than one-third of days from first use.

Alcohol and Drug Use Confirmation Tests

Breathalyzer (for alcohol) and urine (for drug) samples were collected at postintervention and follow-up. We calculated agreement rates for any and each drug (excluding alcohol) against TLFB self-report. Only two participants had a positive Breathalyzer result. For urinalysis, we compared TLFB drug use reports for 3 days before the urinalysis date against the urinalysis result.

Data Analysis

Our analytic sample size of 200 was powered to detect a medium-sized effect (Cox regression hazard ratio [HR] = 0.51) for days until first drug use with a two-sided $p < .05$ significance level,

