80% power, and a 35% probability of substance use in the control group. Our ITT analysis of $N = 200$ did not include the 25 women randomized to a study group who never showed up to the first class and were thus excluded from analysis based on receiving no dose of the intervention. Prediction models included clinical covariates identified a priori as having conceptual relevance for their impact on the effect of study intervention on recovery (i.e., number of mental health diagnoses coded as SUD only, one co-morbid mental health diagnosis, two or more comorbid mental health diagnoses, adult- hood trauma exposure [summed domain score from Life Stressor Checklist Revised], PTSD diagnosis via the Diagnostic and Statistical Manual of Mental Disorders [5th Edition], and PTSD symptom score [PTSD symptom Scale Self Report]). These models also adjust for an inherent study design variable (i.e., days in residential treatment before study intervention start date). Unadjusted models as effect size confirmation is located in the online supplement. We use the piecewise Cox regression PHREG procedure in SAS version 9.4 (SAS Institute) to model time periods during and after the study intervention (i.e., piece 1 predicting outcome events during the intervention period and piece 2 predicting outcome events after the intervention). Resulting HR effect sizes are interpreted as small (0.77), medium (0.53), and large (0.36) (35). Next, because of the zero-inflated distribution of days of substance use, we use negative binomial hurdle models to estimate any use (versus abstinence) and days of use among users simultaneously (36). Finally, we compute unadjusted and adjusted proportional estimates for group differences in relapse status (i.e., abstinent, lapse, relapse), and effect size is expressed as odds ratios (ORs).

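### Substance use: up to 15 group comparisons, none named as confirmatory and no multiplicity rule, so the chance of a false substance-use claim is well above 5%

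*SAP*

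**What the plan says.** The SAP section Substance Use and Relapse uses the timeline follow-back data to define "three substance use outcomes for any drug use and alcohol to intoxication as well as methamphetamine and cannabis/marijuana". The three outcomes are time to first use, days of use and relapse status.

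The Data Analysis section that follows the alcohol and drug confirmation tests gives one sizing statement: "Our analytic sample size of 200 was powered to detect a medium-sized effect (Cox regression hazard ratio [HR] = 0.51". The sizing outcome is the time to first drug use, tested two-sided at .05, and the remaining inputs are "80% power, and a 35% probability of substance use in the control group". It then sets out three analyses:

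- Time to first use: a piecewise Cox model, "piece 1 predicting outcome events during the intervention period and piece 2 predicting outcome events after the intervention".
- Days of use: "we use negative binomial hurdle models to estimate any use (versus abstinence) and days of use among users simultaneously".
- Relapse status: "we compute unadjusted and adjusted proportional estimates for group differences in relapse status (i.e., abstinent, lapse, relapse", with odds ratios as the effect size.

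Neither section calls any substance-use outcome primary, secondary or exploratory. Neither sets an order of testing or mentions multiplicity. Elsewhere, the protocol's Study design section says the trial was designed to compare retention in residential treatment. The SAP's first Data analysis section gives retention its own power calculation, also at a two-sided 5% level and 80% power.

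**The concern.** A plan that yields many comparisons on one question, and does not say which of them answers it, lets any nominally significant result be presented as the answer. Here the question is whether MMWR reduced substance use. The substance-use outcomes have their own power statement, in the same form as the one for retention, so a reader could take a positive result on any of them as confirmatory.

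The power statement does not settle the matter. It sizes for one hazard ratio, while the planned model gives two, one during and one after the intervention. It also speaks of days until first drug use, while the outcome definition counts alcohol intoxication as well. Even for the powered outcome, the reader cannot tell which estimate carries the claim.

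**Working it through.** **1. The plan's own figure.** Inputs from the substance-use Data Analysis section: HR 0.51, two-sided .05, 80% power, 35% use, N = 200. Equal allocation is assumed, since no ratio is stated. Events needed (Schoenfeld) = 4 × (1.960 + 0.842)² / (ln 0.51)² = 69.2, so 70. Then 70 / 0.35 = 200. The stated N is reproduced if 35% is the overall probability of use; the text words it as the control-group probability, which is a separate matter. The sizing therefore rests on one test of one hazard ratio.

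**2. Count of comparisons.** Per substance group: 2 Cox pieces + 2 hurdle parts + 1 relapse-status comparison = 5. With three substance groups: 3 × 5 = 15. The analysis text does not say that every model is run for every substance, so 15 is the upper count; 5 applies if only any drug or alcohol to intoxication is modelled. Adjusted and unadjusted versions of a comparison are counted once.

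**3. False-positive chance if independent.** With each comparison read at .05 and no effect on any outcome, the chance of at least one false positive is 1 − 0.95^k:

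- k = 15: 1 − 0.95^15 = 53.7%
- k = 5: 1 − 0.95^5 = 22.6%

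**4. With correlation.** The documents give no correlation, so this is an assumed range. Each test statistic was simulated as √ρ × (a shared normal) + √(1 − ρ) × (its own normal), in 400,000 draws, counting draws in which any absolute value exceeds 1.96.

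| Common correlation | 15 tests | 5 tests |
|---|---|---|
| 0 | 54% | 23% |
| .3 | 46% | 21% |
| .5 | 36% | 18% |
| .7 | 26% | 15% |
| .9 | 14% | 10% |

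**5. The powered outcome alone.** The two Cox pieces use events from separate periods, so under no effect their tests are taken as approximately independent. If either counts: 1 − 0.95² = 9.75%, about twice the nominal level.

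**6. What designation does and does not cost.** One confirmatory test at .05 holds the error for that claim at 5% and leaves the sizing at 70 events. Treating all 15 as confirmatory with Bonferroni means .05 / 15 = .0033 each. Power at 70 events for HR 0.51 then falls from 80.4% to 45%, and 80% power would need 126 events, or 126 / 0.35 = 360 women.

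**The case against.** The strongest reply is that the plan does have a lead outcome. Its power statement singles out days until first drug use, and the protocol makes retention the design objective, so the substance-use results can be read as subordinate and formal error control across them as a matter of preference. Much of this stands: the SAP points to one outcome without labelling it. It does not settle which of two hazard ratios decides, and the SAP nowhere calls the other comparisons secondary.

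A second reply also stands: .05 is stated only for sizing. The analysis text interprets hazard ratios by size and gives odds ratios as effect sizes, without a decision rule. Reading each comparison at .05 is an inference, though no other threshold is offered.

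Third, the tests overlap. Any-drug use contains methamphetamine and cannabis use, and time to first use, the any-use hurdle part and abstinent status all draw on the same first-use information. Positive correlation is therefore expected, and the independent figures are best taken as the top of the range.

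A reader might infer two stronger things. One is a count of 18 (three outcomes by three substances by two model parts). The documents do not support it: relapse status has no two-part model, and 18 requires splitting its three levels into two contrasts that the SAP does not state. The other is that a false-positive claim is likely. For 15 tests the chance passes 50% only near independence; it is already 46% at a correlation of .3.

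**Conclusion.** The point holds in this form: the substance-use plan supports between 5 and 15 group comparisons, with no designated confirmatory test and no multiplicity control. The chance of at least one false positive is above 5% under every assumption tried: 14% to 54% for 15 tests and 10% to 23% for 5, over common correlations from .9 down to 0. For the two Cox pieces of a single outcome it is about 10%.

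These figures assume no effect on any substance-use outcome, a .05 reading of each comparison, and correlations that are not in the documents. They show that nominal significance on one of these comparisons is weak evidence by itself. They do not show that a false claim is more likely than not, or that the plan lacks any indication of a lead outcome.

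**What to change.** Name one confirmatory substance-use test at two-sided .05: time to first use of any drug or alcohol to intoxication, as one stated contrast. That contrast can be a single overall test across both periods or one named Cox piece. Align the wording of the power statement with the outcome definition, so that it is clear whether alcohol intoxication counts.

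Label every other substance-use comparison secondary or exploratory: the other Cox piece or pieces, both hurdle parts, relapse status, and all methamphetamine and cannabis results. Report these with estimates and confidence intervals and no significance claims, or adjust them by Holm.

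The SAP already describes observed data: retention curves that crossed at 50 days, and two positive Breathalyzer results. A designation made now cannot be presented as blind to results. State that it rests on the power statement, and disclose when it was made.

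The cost is SAP wording, with no change to the stated N. Some secondary p-values can no longer be reported as significant effects. If one Cox piece is chosen over an overall test, and the 35% refers to the whole follow-up, that piece will hold only part of the 70 events, so the stated 80% power would not carry over to it.

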### *Interventions*

#### ***Moment-by-Moment in Women's recovery (MMWR)***

This intervention was delivered twice weekly for 80 min each for a total of 12 group sessions (6 weeks) during residential treatment. MMWR was guided by an instructional manual with

standardized lesson plans. An experienced teacher trained in both MBSR and MMWR facilitated all sessions along with an on-site masters-level clinician with experience in SUDs who co-facilitated the intervention. Each class session had a central theme divided into five segments in the following general order: (1) welcome, review of group culture, brief homework practice check-in, objectives, and brief mindfulness meditation or practice; (2) didactic psychoeducational presentation and discussion of lesson content; 3) experiential meditation and mindfulness practices related to the session's theme; (4) practice of sitting or walking meditation, body scan, and/or standing stretching; and (5) selected reading related to session topic, assignments for the next class, and closing meditation. Trainees were expected to learn skills to approach experiences and stressors using mindfulness principles. Students learned about the role of automatic reactivity to stressors and its relation to addiction and relapse; the connections between stress, triggers, and relapse; and how to use mindfulness practices to respond best to related thoughts, emotions, body sensations (including those related to stress in a residential treatment setting that could lead to treatment dropout), and triggers while still avoiding relapse. As with MBSR, trainees learned and practiced self-regulation strategies using four foundational mindfulness practices. Teachers instructed on the use of formal (audio- guided sitting meditation, sitting meditation without audio, loving kindness meditation, walking meditation, body scan, and mindful stretching) and informal practices (stop light technique, triangle of awareness, mindfulness of breath, mindfulness of emotions, mind- fulness of thoughts, mindfulness of body sensations, and mindfulness of cravings). Throughout the course, students were encouraged to bring mindful awareness into their daily activities by using informal practices and to engage in formal meditation practices as homework in accordance with practice assignments and guided meditation audio recordings. Participants received a MMWR Participant Workbook at the beginning of the course organized by session, containing key concepts and practices introduced in each session, and homework and practice assignments for each session. Participants were asked to bring their Workbook to each session so that they

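### Urine and breath results enter no substance-use outcome, so a positive test inside the outcome window with no reported use is analysed as abstinence and any under-reporting is left uncorrected

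*SAP*

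**What the plan says.** The SAP section on substance use and relapse takes every substance-use outcome from the TLFB interview: "TLFB data allowed us to operationalize three substance use outcomes for any drug use and alcohol to intoxication". The lowest relapse category is "abstinent, did not use during the period after the study intervention", with no test condition attached.

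The section on confirmation tests states that "Breathalyzer (for alcohol) and urine (for drug) samples were collected at postintervention and follow-up". It gives urine one role: "We calculated agreement rates for any and each drug (excluding alcohol) against TLFB self-report". The comparison is short: "we compared TLFB drug use reports for 3 days before the urinalysis date against the urinalysis result". On breath tests it says only "Only two participants had a positive Breathalyzer result", with no rule for those two women.

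The data analysis section that follows describes a piecewise Cox model, a negative binomial hurdle model and a comparison of relapse categories. None of them uses a test result. The SAP gives no rule for discordant cases, no sensitivity analysis based on tests, no agreement by arm and no rule for missing samples.

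On knowledge of assignment, the protocol describes two visibly different classes, each with its own named materials, for example "Participants received a MMWR Participant Workbook at the beginning of the course organized by session". Whether the TLFB interviewers were blinded is not described.

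**The concern.** The trial holds objective evidence on its outcome at two visits and uses it only to describe the quality of self-report. A woman whose sample is positive for a period she reported as drug-free keeps her self-reported status in all three analyses.

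This matters most if under-reporting differs by arm. The protocol makes that possible without showing it. MMWR taught women to handle triggers without relapsing, while the NA sessions left out behaviour change and relapse content, so only one arm was coached towards the outcome it later reported. Women in residence in either arm also had a reason to under-report, since the SAP lists repeated relapse as a ground for administrative discharge; that reason is not specific to an arm. Concealment confined to MMWR would push time to first use, any use and relapse status in that arm's favour. Equal concealment would mainly cost events and power.

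**Working it through.** **1. What happens to a discordant woman.** Take a positive urine test whose 3-day window lies inside the outcome period, with no use reported on TLFB. Following the SAP as written:
- relapse status: abstinent, because the category rests on TLFB;
- hurdle model: non-user with zero days;
- Cox model: no event.

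**2. The plan's own figure.** The substance-use analysis states N = 200 for HR 0.51, two-sided 5%, 80% power and 35% use. Schoenfeld: 4 × (1.960 + 0.842)² / (ln 0.51)² = 31.40 / 0.4534 = 69.25, rounded up to 70 events; 70 / 0.35 = 200. This reproduces N if 35% is the overall event probability. The point does not depend on N; the 35% is borrowed below as a plausible level of use.

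**3. Illustration with odds ratios (concealment assumed).** True use is 35% in both arms, with full reporting in NA.
- 5 points concealed in MMWR: (0.30/0.70) / (0.35/0.65) = 0.80.
- 10 points concealed in MMWR: (0.25/0.75) / (0.35/0.65) = 0.62.

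These mean that 5/35 = 14% and 10/35 = 29% of MMWR users conceal, and nobody in NA does.

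**4. The same on the hazard-ratio scale.** Assume 100 women per arm and no true effect. Observed HR = ln(1 − observed MMWR use) / ln(0.65).

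| MMWR users concealing | Observed use | Observed HR | Chance of a significant result favouring MMWR |
|---|---|---|---|
| 0% | 35.0% | 1.00 | 2.5% |
| 10% | 31.5% | 0.88 | about 8% |
| 20% | 28.0% | 0.76 | about 19% |
| 30% | 24.5% | 0.65 | about 38% |

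The 20% row is 7 of 35 women and lands next to the SAP's own benchmark for a small effect, 0.77.

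**5. Equal concealment.** With a true HR of 0.51 and 35% read as the control-arm rate, 10% or 20% concealment in both arms leaves the observed HR at about 0.52. Power falls from 70% to 64% or 57%.

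**6. How much the tests can reach.** The SAP gives "8.5-month follow-up period in total": 8.5 × 30.4 = 258 days. Two windows of 3 days are 6 days, and 6/258 = 2.3%. If each test detects exactly its 3-day window, a single concealed day placed at random has about a 2.3% chance of being caught, whereas a woman using daily around a visit would be caught if she gave a sample.

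**7. Timing.** Postintervention samples fall between day 1 and day 14 after the last session. For a sample on day *d*, the window is days *d* − 3 to *d* − 1. It lies wholly after the last session (day 0) only if *d* is 4 or more; samples on days 1 to 3 may reflect use during the intervention. Follow-up visits fall in months 7 to 9, while use is first said to be counted for 7 months and then said to be quantified to the study end point. A month-8 sample may therefore lie outside the outcome period.

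**The case against.** The strongest reply has four parts.

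- **Differential concealment is assumed.** Both classes are active and are described as matched on time, attention and expected benefit. The one explicit statement that blinding was impossible concerns the discharge team and the retention outcome. This stands. A reader might infer that biased reporting in favour of MMWR is present; the documents do not support that, because they report no agreement rate or discordant count, overall or by arm. They do show that under-reporting, if it occurred, is not corrected.
- **A positive test need not contradict abstinence.** This also stands. Early postintervention samples and late follow-up samples may reflect use outside the post-intervention outcome period, so the point is limited to in-window positives. Counting every positive as a lapse would create errors of its own.
- **The odds ratios overstate what recoding can achieve.** They do if read as correctable bias. 0.80 and 0.62 describe assumed concealment over the whole follow-up, and two short checks would leave most of it in place. They are not estimates for this trial.
- **TLFB is a validated interview given by trained staff, and it was checked against tests.** True, but an overall agreement rate changes no one's coding and does not show whether agreement is the same in both arms.

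These replies narrow the claim and shape the remedy. None supplies a rule for the in-window discordant woman.

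**Conclusion.** The point holds in limited form. On the stated plan, objective results already in hand enter no substance-use outcome, and a woman with an in-window positive test and no reported use is analysed as abstinent. That women knew their class is inferred from the design of the classes.

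The size of any effect on the results is unknown. It depends on how many women are discordant, in which arm, and how many samples are missing, none of which the documents report. The illustrative range runs from almost no change in the hazard ratio under equal concealment to an apparent small effect where none exists if about one in five users in one arm conceals.

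This is a cheap improvement to the analysis. It is not evidence that the substance-use findings are wrong.

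**What to change.** Keep TLFB as the main analysis and add one sensitivity analysis of time to first use, any use and relapse status in which a positive urine or Breathalyzer test counts as use. Date first use to the sample day if nothing earlier was reported.

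- **Relapse category.** State in advance that a recoded woman is at least a lapse. The one-third rule says little when the only known use is a single tested day.
- **Postintervention positives.** For relapse status and piece 2 of the Cox model, count them only if the 3-day window lies wholly after the last session; otherwise assign them to the intervention period.
- **Follow-up positives.** Count them only within the analysed outcome period, and state whether that period ends at 7 months or at the interview date.
- **Reporting.** Give agreement, discordant counts and missing samples by arm, and say whether the TLFB interviewers were blinded. Show the recoded estimates with confidence intervals beside the TLFB results, and qualify the substance-use conclusion if they differ materially.

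The SAP already reports a test result, so the analysis should be labelled as added after data were available.

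The cost is a recode of existing data and one re-run. The drawbacks are that tests exist at two visits only, so the correction is partial; dates of first use are approximate for recoded women; and unequal sample return by arm could itself move the recoded result.

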## **Study Protocol**

### ***Study design***

This parallel-group RCT was designed to compare retention days in residential treatment among participants randomly assigned to one of two study conditions as adjuncts to their residential SUD treatment: (1) MMWR and (2) Neurobiology of Addiction (NA), with the latter serving as the psychoeducational control condition. Baseline interviews occurred prior to randomization and post-intervention interviews occurred up to 14 days after the last class session of the study intervention. All participants received SUD treatment services as normally provided by the treatment facility without affecting the level of usual care provided to patients. The study site offered no structured mindfulness-based activities or services during the study period. The University of Southern California Institutional Review Board approved this study (UP-14-00391).

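### The substance-use power statement does not follow from its own inputs: 200 women with 35% control-group use give about 55 events and roughly 70% power for HR 0.51, not 80%

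*SAP*

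**What the plan says.** The power statement for time to first use opens the Data Analysis section that follows Substance Use and Relapse in the SAP. It says: "Our analytic sample size of 200 was powered to detect a medium-sized effect (Cox regression hazard ratio [HR] = 0.51", "with a two-sided $p < .05$ significance level", with 80% power and "a 35% probability of substance use in the control group". The 35% is therefore a probability of use, not of abstinence, and it belongs to the control arm, not to the pooled sample.

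The statement gives no event count, formula, allocation ratio, time point for the 35%, or allowance for loss to follow-up. The same section says that the 200 already exclude 25 randomized women who never attended a class, and that the analysis is a two-piece Cox model (during and after the intervention).

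**The concern.** Power for a hazard ratio depends on the number of events in both arms together. If the intervention halves the hazard, the MMWR arm contributes far fewer events than the control arm. A 35% control rate then cannot produce a 35% event rate overall. The stated 80% looks as though this was overlooked.

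At stake is how a null result for time to first use would be read. With 70% power the chance of missing a true HR of 0.51 is about 30%, not 20%, so a non-significant result is weaker evidence against a medium-sized effect than the SAP implies. The two-piece model makes this worse, because it divides the events between two hazard ratios.

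**Working it through.** **Inputs.** From the SAP: N = 200, HR = 0.51, two-sided 5% level, 80% power, 35% use in the control group. Assumed: 1:1 allocation (the Protocol's Study design says only "participants randomly assigned to one of two study conditions"), proportional hazards, 35% cumulative over the whole follow-up, and no loss before its end. Here z = 1.960 + 0.842 = 2.802 and ln(0.51) = −0.673.

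**Events needed for 80% power at HR 0.51**
- Schoenfeld: d = 4z²/(ln HR)² = 4 × 2.802²/0.673² = 69.2, so 70.
- Freedman: d = z²[(1 + HR)/(1 − HR)]² = 2.802² × (1.51/0.49)² = 74.5, so 75.

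**Reproducing the plan's figure.** If 35% is applied to all 200 women, events = 0.35 × 200 = 70. Schoenfeld power is Φ(0.673 × √70/2 − 1.960) = 80.4%, and the HR detectable with 80% power is exp(−2 × 2.802/√70) = 0.512. In reverse, 70/0.35 = 200 exactly. The stated numbers return when 35% is the pooled event probability.

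**Using the inputs as written**
- MMWR-arm probability: 1 − (1 − 0.35)^0.51 = 0.197.
- Average probability: (0.350 + 0.197)/2 = 0.2736.
- Events: 200 × 0.2736 = 54.7.
- Schoenfeld power: Φ(0.673 × √54.7/2 − 1.960) = Φ(0.531) = 70.2%.
- Freedman power: Φ(√54.7 × 0.49/1.51 − 1.960) = Φ(0.441) = 67.0%.
- Log-rank simulation (1:1, administrative censoring only, 10,000 runs): 68.7%.
- Two-proportion test of 35% against 19.7%: 68.1%.

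**Detectable HR and required N.** Solving for 80% power with N = 200 and 35% control use gives an HR of 0.46 (Schoenfeld) or 0.44 (Freedman). Keeping HR 0.51 needs 69.2/0.2736 = 253 women (Schoenfeld) or 74.5/0.2736 = 272 (Freedman). Rounding the events up first gives 256 or 274.

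**Other readings tried**

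| Reading | Power | Fits the text? |
|---|---|---|
| 35% pooled over both arms | 80.4% | No: text says control group |
| One-sided 5% | 80.1% | No: text says two-sided |
| 0.51 as a risk ratio (35% vs 17.85%) | 79.0% | No: text says Cox HR |
| 35% abstinent in control (65% use) | 93.5% | No: text says use |
| All 225 randomized women | 75% | No: text says 200 |
| Most favourable allocation (about 57% control) | 71% | Not excluded, but short of 80% |

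**If 35% is the pooled rate.** An average of 35% at HR 0.51 requires about 44% use in the control arm (44.2% and 25.8% average 35%). That is a different planning assumption from the one written.

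**Internal comparison.** The SAP's retention power statement, which uses 50% control retention, reproduces approximately by Freedman with the same proportional-hazards step: detectable HR 0.524 at N = 200 and 0.547 at N = 225, against the stated 0.52 to 0.54. The mismatch is therefore specific to the substance-use statement.

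**Per piece (illustration only).** With a constant hazard over the "8.5-month follow-up period in total", the six-week intervention piece would have about 10 events (19% power at HR 0.51) and the later piece about 44 (61%).

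**The case against.** The strongest counter-argument is that the 35% has no time point. If it referred to an earlier time than the end of follow-up, more events would accrue. At constant hazard and HR 0.51, 35% at 6 months followed to 8.5 months gives 72.4 events and 82% power by Schoenfeld (79% by Freedman). With 35% at 7 months followed to 8.5, or 35% at 8.5 months followed to 10.5, power is about 77%. So one can construct a control-group reading that reaches about 80%. This shows that the horizon must be stated, but nothing in the documents supports a 6-month figure, so it does not rescue the sentence as written.

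The cause is also an inference. The match at 70 events is exact, yet a one-sided test and a risk-ratio reading come close too. If a pooled rate was simply mislabelled, 80% is right and only the label is wrong. That stands, and the fix allows for it.

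It can further be said that the Protocol designed the trial around retention, that N was already fixed when the SAP was dated, and that a null result will be judged mainly by its confidence interval. All fair: the error biases no estimate and alters no model. It still leaves a stated design property that the stated inputs do not deliver.

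Finally, the per-piece powers need a constant hazard that no section supports, and the SAP never claims 80% for each piece. They are illustrative and the finding does not depend on them.

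**Conclusion.** The concern holds. As written, the inputs give about 55 events and 67% to 70% power, some 10 to 13 percentage points below the stated 80%. The HR detectable with 80% power is about 0.44 to 0.46, not 0.51. Either the power or the label on the 35% is wrong.

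This rests on proportional hazards, 1:1 allocation and 35% being cumulative to the end of follow-up. Allocation cannot close the gap; an earlier horizon for the 35% could, but the SAP states none. Any loss to follow-up would lower power further. That a pooled rate was described as the control rate is the likeliest explanation, but it is not established.

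**What to change.** Correct the sentence in one of two ways, according to what was meant:

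- **35% is the control rate:** state that 200 women give about 70% power for HR 0.51, and that the HR detectable with 80% power is about 0.46.
- **35% is the pooled rate:** say so, keep the 80%, and state that it implies about 44% use in the control arm.

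In both cases add the expected number of events, the formula used and the time over which the 35% accrues. Say too that the power refers to a single overall hazard ratio, not to each piece of the two-piece model.

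The cost is a sentence or two in the SAP. Enrolment and the analysis model stay as they are. Under the first option the stated sensitivity becomes less favourable; under the second the control-rate assumption rises from 35% to about 44% and has to be justified.
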